4.6 Data Sources

Data for this study will be obtained via the following sources:

- Patient medical file: The investigator or authorised medical staff will record clinical and treatment data (if applicable) from patients' medical files into the eCRF at each collection time point, specified in Table 4-1.
- Tumour assessments: All tumour assessments are based on investigator's clinical and/or assessments by imaging. For radiological assessments tumour imaging data is provided by the radiologists. Data is recorded in the eCRF at each collection time point, specified in Table 4-1.

PAGE 27/52

- Quality of Life (QoL) questionnaire: EORTC QLQ-C30 (Version 3, German language) and QLQ-GINET21 (2006, German language) questionnaire data will be collected on paper-based questionnaires or electronic version if used per treatment routine in the site and completed by the participant at each collection time point. The investigator or authorised medical staff will record the data into the eCRF at each collection time point, specified in Table 4-1.
- NET Biomarkers: NET Biomarker data for CgA and NSE are provided by the centre's local laboratory and recorded in the eCRF at collection time points when available, specified in Table 4-1.

4.7 Study Duration/Observation Period

The expected study duration is 3 years, with an 18-month enrolment period from first participant, first visit. The EoS is expected to be a maximum 18 months after the last participant has been enrolled.

The study will be considered to have started when the first participant has signed informed consent.

The study will be considered to have ended after the last participant's data has been collected.

The study observation period starts from participants signing the informed consent and continues until Visit 9 (Month 18). Participants discontinuing cabozantinib treatment and starting a new LoT during the first 15 months of cabozantinib treatment are passing over into the follow-up, which is approximately 3 months after discontinuation of cabozantinib.

Participants will be followed until the end of observational period (i.e. a maximum of 18 months after Visit 1) or withdrawal of consent, or death, whichever occurs first.

4.8 Participant Information

Prior to enrolment of a participant in this study, the investigator, or a person designated by the investigator, will explain the nature and purpose of this data collection to each participant. As all assessments and procedures will be conducted in accordance with routine/standard clinical practice, participation in the study does not convey any additional risks or burdens for the participant. However, the participant will be provided with information on the benefits and risks of their medical treatment.

Written informed consent must be obtained prior to participant enrolment and prior to any data being entered in the study database. Sufficient time should be allowed to discuss any questions raised by the participant. The participant should be allowed as much time as they need to consider their decision.

The sponsor will provide an informed consent form (ICF), in German language easily understood by the participant. Each participant's original consent form, personally signed and dated by the participant, and by the person who conducted the informed consent discussion, will be retained by the investigator. The investigator will supply all enrolled participants with a copy of their signed informed consent. None of these informed consents will be collected by the sponsor.

The consent form will be revised during the study if important new information becomes available.

PAGE 28/52

5 STUDY POPULATION

Study sites will include oncology practices, hospitals, and Academic Medical Centres as well as ENETS Centres of Excellence. This prospective study will include participants who meet all eligibility criteria.

5.1 Inclusion Criteria

Patients are eligible to be included in the study only if all the following criteria apply:

- 1. Participant aged ≥ 8 years with capacity to consent.
- 2. Physician-initiated decision to treat with cabozantinib for NET (prior to study enrolment) according to SmPC.
- 3. Signed written informed consent.

5.2 Exclusion Criteria

Patients will not be included in the study if they meet any of the following criteria:

- 1. Participation in an interventional trial at the same time and/or within 3 months before baseline.
- 2. Contraindication for cabozantinib treatment according to SmPC.

5.3 Participant Withdrawal Criteria

As this is a non-interventional study, participants will be managed according to each clinical site's medical routine/standard practice, therefore no specific withdrawal criteria are specified.

Participants are free to withdraw consent at any time. The investigator may withdraw a participant from the study at any time for safety reasons or at his/her discretion. Data will be collected up to the time of withdrawal, with no additional information collected thereafter.

For participants who withdraw from the study, withdrawal details are recorded in the specific section of the eCRF of the next planned collection time point. Any AEs collected/reported will, however, be followed-up until resolved or stabilised or until the participant is lost to follow up (a participant is considered lost to follow-up if the centre was repeatedly unable to contact the participant e.g. by phone or email).

In case the participant is withdrawn from the study, the primary reason for withdrawal should be recorded in the eCRF.

PAGE 29/52

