8.4.3 Effectiveness Analysis

8.4.3.1 Primary Effectiveness Analysis

The primary endpoint is the DCR at 6 months, defined as the proportion of participants who, within 6 months achieve CR, PR or SD determined based on radiographic assessments between the date of the first dose of cabozantinib until the date of progressive disease (PD) or date of subsequent therapy.

The proportion of participants with DCR will be calculated by counting all participants who have SD, PR or CR at any post-baseline TA and dividing them by the number of participants in the FAS with at least one post-baseline TA. Participants who are treated with cabozantinib beyond progression but have not had SD, PR or CR prior to disease progression, will be considered to have no SD, PR or CR, even if they achieve SD, PR or CR after PD. DCR will be provided with the corresponding 95% CI.

In a secondary analysis, the DCR will be calculated similarly except that the count of participants who have SD, PR or CR at any post-baseline TA will be divided by the number of participants in the FAS.

PROTOCOL FINAL V1.0: 30 JULY 2025

PAGE 35/52

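### Section 5.3 lets the investigator end observation for safety reasons in a study that says it adds no risk; if used for toxicity, later outcome data are lost informatively

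*Protocol*

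**What the plan says.** Section 5.3 of the protocol first says that no specific withdrawal criteria are set. It then provides that "The investigator may withdraw a participant from the study at any time for safety reasons or at his/her discretion". The consequence is that "Data will be collected up to the time of withdrawal, with no additional information collected thereafter". There are two qualifications in the same section: "Any AEs collected/reported will, however, be followed-up until resolved or stabilised or until the participant is lost to follow up", and "the primary reason for withdrawal should be recorded in the eCRF".

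Three other places bear on this:

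- Section 4.8 tells participants that "participation in the study does not convey any additional risks or burdens for the participant".
- Section 4.7 follows each participant to the end of the observation period "or withdrawal of consent, or death, whichever occurs first". Neither investigator withdrawal nor loss to follow-up is in that list.
- In Table 4-1, footnote f treats stopping cabozantinib for intolerability or AEs as a treatment discontinuation, with an FU visit if therapy is switched. Footnote g, attached to the cabozantinib regimen row, lists permanent discontinuation of the study beside dose modifications and interruptions.

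For the primary DCR, Section 8.4.3.1 counts participants with SD, PR or CR, "dividing them by the number of participants in the FAS with at least one post-baseline TA". A secondary analysis uses a count that "will be divided by the number of participants in the FAS".

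**The concern.** The clause concerns leaving the study, not stopping the drug. Prescribing is independent of enrolment and the study adds no procedures, so ending observation protects no one. A safety ground for withdrawal makes sense where the protocol gives the treatment; here it has no clear function. Footnote g makes it easier for a site to treat a toxicity stop and a study exit as the same event, and Section 5.3 does not say that they differ.

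If the clause is used that way, the participants lost are those with poor tolerability. Their later progression, death, new AEs, dose changes and next-line therapy are not recorded. The Kaplan-Meier estimate of PFS would then be censored for a reason that may be related to prognosis, and no rule in the SAP can restore events that were never collected. Section 4.5 expects imaging about every 3 months, and Table 4-1 places the first post-baseline assessment at Month 3. A participant withdrawn for early toxicity can therefore leave before any scan and drop out of the primary DCR denominator.

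**Working it through.** **1. The passages side by side.** Section 5.3 permits investigator withdrawal, Section 4.7 does not mention it, and Section 4.8 removes the rationale for its safety ground. Footnote f keeps treatment stop and study exit apart; footnote g merges them. Section 8.1 defines switched and withdrawn participants separately, which agrees with footnote f. The design mostly intends the distinction, but Section 5.3 and footnote g do not carry it through.

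**2. The plan's own figures (Section 8.3).**

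- Evaluable: 150 × (1 − 0.10) = 135, so 15 planned dropouts.
- Expected DCR: (51 + 94)/(64 + 134) = 145/198 = 73.2%, given as 73%.
- 95% half-width: 1.96 × √(0.73 × 0.27/135) = 0.0749. The stated ±7.5% is reproduced.

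**3. Possible effect on the primary DCR.** Let k of 150 treated participants leave before a first post-baseline assessment. Let the other 150 − k all be assessed, with DCR p = 0.73, and let the leavers have true DCR q. The primary rule estimates p. The rate in all 150 is [(150 − k)p + kq]/150. The excess is therefore

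(k/150) × (p − q).

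The protocol gives neither the number of safety withdrawals nor their DCR, so k and q are assumed ranges. The excess in percentage points is:

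| k | q = 0 | q = 0.30 | q = 0.50 | q = 0.73 |
|---|---|---|---|---|
| 3 | 1.5 | 0.9 | 0.5 | 0 |
| 5 | 2.4 | 1.4 | 0.8 | 0 |
| 10 | 4.9 | 2.9 | 1.5 | 0 |
| 15 | 7.3 | 4.3 | 2.3 | 0 |

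For example, k = 15 and q = 0 gives (15/150) × 0.73 = 7.3 points, about the size of the planned half-width. That corner requires every planned dropout to leave before a scan and none to have disease control.

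**4. What the whole-FAS analysis shows.** With k = 15, 0.73 × 135 = 98.55, or 99 participants with disease control. The primary rule gives 99/135 = 73.3%; the whole-FAS rule gives 99/150 = 66.0%. The gap of 7.3 points bounds the effect, because the whole-FAS rule scores every leaver as without disease control. It does not recover their outcomes.

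**The case against.** The case on the other side is substantial, and much of it stands.

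- **The clause is permissive.** A reader might infer that sites would withdraw participants with severe toxicity. The text says only that they may. Footnote f sends toxicity stops to treatment discontinuation and the FU visit, and Section 4.1 admits patients who stopped within 4 weeks precisely to limit selection bias. Systematic removal is not in the documents; its possibility is.
- **Safety endpoints.** A reader might infer that these participants are lost to the safety analysis. They are not. The Safety population is all eligible treated participants (Section 8.2), and AEs already recorded are kept and followed. Only new events after withdrawal are missed, and from 30 days after stopping the drug only cabozantinib-related events are collected for anyone (Section 9.2).
- **Section 4.7.** A reader might infer a flat contradiction. Section 4.7 does not say that follow-up ends only in the listed ways, and it also omits loss to follow-up. It is better read as an incomplete list that needs aligning.
- **DCR.** The distortion arises mainly from the Section 8.4.3.1 denominator, which affects any participant without a scan. The whole-FAS analysis is already planned, and anyone scanned before withdrawal stays in. Continued observation would not rescue every case: after a switch before the first scan, later assessments fall outside the DCR window.
- **Visibility.** The reason for withdrawal is recorded and tabulated (Section 8.4.2), so misuse could be seen. That allows the loss to be counted, not repaired.
- **Discretion.** Investigator withdrawal may have legitimate uses, such as ineligibility found later. Deleting it altogether would go too far.

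None of this gives the safety ground a purpose in an observational study, or makes Section 5.3 say that stopping the drug is not leaving the study.

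**Conclusion.** The point holds as a wording defect with a real but unquantified consequence. Section 5.3 permits observation to end on a ground that Section 4.8 makes inapplicable, and Section 4.7 and footnote g do not fit with it. If the clause is used for toxicity, progression, death, new AEs and next-line data after withdrawal are lost, and PFS censoring becomes informative.

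The effect on the primary DCR is between 0 and about 7 points upward. This assumes that at most the 15 planned dropouts leave before a first assessment, that everyone else is assessed with a DCR of 73%, and that the leavers do no better than the rest. No narrower figure is supported, because the protocol does not split the 10% dropout by cause and toxicity does not imply absence of stable disease. The documents do not support saying that these participants disappear from the safety analysis or that a DCR bias of a particular size is to be expected.

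**What to change.** - In Section 5.3, delete safety as a ground for ending observation. State that stopping cabozantinib for any reason, including toxicity, is not study withdrawal, and that routine-care data collection continues as in Section 4.7 and through the FU visit.
- Limit investigator-initiated withdrawal to documented reasons unrelated to outcome, for example ineligibility found later.
- In Section 4.7, add loss to follow-up and any investigator withdrawal that is retained.
- In Table 4-1 footnote g, refer to permanent discontinuation of treatment instead of the study.

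These changes concern data collection only. They leave treatment decisions and the participant's right to withdraw consent untouched. The cost is a protocol wording change and alignment of the eCRF guidance. The downside is that sites keep documenting routine data for a few participants they might otherwise have closed. The changes do not alter the primary DCR denominator, so the whole-FAS DCR should be reported beside the primary result.

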6 STUDY ENDPOINT AND EVALUATIONS

6.1 Effectiveness Endpoints and Evaluations

All effectiveness data are collected as per local routine. Effectiveness assessments are based on clinical and/or tumour assessment via imaging of the disease status.

6.1.1 Primary Effectiveness Endpoint

Disease control rate (DCR):

DCR is defined as proportion of participants who within 6 months achieve complete response (CR), partial response (PR) or stable disease (SD) determined based on radiographic assessments between the date of the first dose of cabozantinib until the date of progressive disease (PD) or date of subsequent therapy.

Disease response definitions:		
CR	Complete response	Complete resolution of all visible disease.
PR	Partial response	Partial reduction in size of visible disease in some or all areas without any areas of increase in visible disease. Captures a decrease in disease volume even though disease is still present.
SD	Stable disease	No change in overall size of visible disease. Also includes cases where some lesions increased in size and some lesions decreased in size.
PD	Progressive disease	Increase in visible disease and/or presence of any new lesions. Includes cases where the clinician indicates PD or progression of disease as the overall assessment.

Table 6-1 Disease response definitions

6.1.2 Secondary Effectiveness Endpoints

Objective response rate (ORR):

ORR is defined as proportion of participants who achieve CR or PR determined based on radiographic assessments between the date of the first dose of cabozantinib and the date of PD or date of subsequent therapy.

Quality of life (hrQoL):

See Section 6.3.

Cabozantinib dosage adjustment and schedule:

- Starting dose, all dose modifications according to frequency, timing, reason for adjustment, type of adjustment and duration of modified dosing, specifically:
 - Frequency of dose reductions and reason (specifically adverse events).
 - Frequency of dose interruptions and reason (specifically adverse events).
 - Frequency of treatment discontinuations and reason (specifically adverse events).

PROTOCOL FINAL V1.0: 30 JULY 2025

PAGE 30/52

Duration of treatment (DoT):

DoT during cabozantinib treatment phase, defined as time from first intake of cabozantinib until date of permanent cabozantinib treatment discontinuation.

Frequency of therapy switch and subsequent therapy:

Frequency of therapy switch is defined as permanent discontinuation of cabozantinib treatment within the cabozantinib treatment phase and start of a next LoT as well as nature of next LoT.

Disease control rate (DCR) after switch to next LoT:

DCR is defined as proportion of participants who within 3 months after switch to next LoT achieve CR, PR or SD determined based on radiographic assessments between the date of the first dose of new treatment until the date of progressive disease (PD) or date of further subsequent therapy.

Time to next treatment (TTNT):

Time from the first dose of cabozantinib to the first dose/administration of the subsequent therapy.

Landmark PFS at 12 months and 18 months:

PFS during cabozantinib treatment phase is defined as time from first intake of cabozantinib until PD (as assessed by the investigator per radiological and/or clinical tumour assessment) or death from any cause. Landmark PFS will be determined at 12 and 18 months and if the number of events allows, the median PFS will be presented.

Biomarker assessments:

Determination of CgA and NSE levels by local labs as per local routine.

- CgA-levels at each visit, CgA was assessed.
- NSE-levels at each visit, NSE was assessed.

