		 DCR of next line of treatment (LoT): proportion of participants who achieve CR, PR or SD determined based on routine radiographic response assess- ments approximately 3 months after switch to next line of therapy after cabozantinib. 				
•	To describe the potential impact of cabozantinib treatment on NET bi-	Chromogranin A (CgA) levels at each visit.				
	omarkers .	Neuron-Specific Enolase (NSE) levels at each visit.				
•	To describe the time to next treatment (TTNT) for cabozantinib.	 TTNT, defined as time from first dose of cabozantinib until first dose of sub- sequent therapy. 				
•	To describe the progression free survival (PFS).	 PFS during cabozantinib treatment phase, defined as time from first in- take of cabozantinib until PD (as as- sessed by the investigator per radio- logical and/or clinical tumour assess- ment) or death from any cause. 				
		• Rate of progression-free survival at 12 months and 18 months.				
Explo	oratory					
•	To describe supporting measures.	Assessment of nature and proportion of participants receiving the different measures at each visit these measures were assessed.				

PAGE 18/52

Objectives	Endpoints				
To describe potential correlations between effectiveness outcomes or quality of life and occurrence of AEs, dose reduction or supportive measures.	 Assessment of a potential correlation between the investigated parameters, specifically: Effectiveness outcomes and occurrence of AEs. Effectiveness outcomes and dose reduction. HrQoL and dose reduction. HrQoL and supporting measures. Supportive measures and DoT/treatment discontinuation due to AEs. Dose reduction and DoT. HrQoL and DoT. see related secondary safety, effectiveness and hrQoL endpoints. 				

PAGE 19/52

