4.1 Overview

This is an international, multicentre, non-interventional, prospective, single-arm study. This study will be conducted in up to 50 centres in Austria and Germany. A total of 150 participants will be included in the study. Participants will be treated and monitored in accordance with usual medical practice during their participation in this study.

The expected duration of the recruitment period will be 18 months. Participants will be followed for a maximum of 18 months (observation period) while they receive cabozantinib as per the SmPC.

Participants prematurely discontinuing cabozantinib (i.e. within the first 15 months of observation period) and initiating a subsequent treatment will be followed up approximately 3 months after the treatment switch to collect effectiveness data for the new LoT. Enrolment in the study is possible if cabozantinib treatment started up to 4 weeks prior to enrolment. The data for Visit 1 will be captured retrospectively and starting at Visit 2 data will be collected prospectively including hrQoL baseline assessment.

To avoid selection bias in participant recruitment, investigators will offer enrolment to all eligible participants consecutively to achieve their recruitment target during a restricted and defined period. This includes patients who have stopped cabozantinib treatment within their first 4 weeks to avoid selection bias. But, if consecutive enrolment is not feasible (e.g. administrative constraints), an alternate enrolment schedule will be permitted and will have to be documented before the first participant is enrolled. The investigators will have to follow the same recruitment pace until achievement of his/her recruitment target.

4.2 **Population Characteristics**

One hundred and fifty (150) adult participants with unresectable or metastatic, well -differentiated epNET and pNET who have progressed following at least one prior systemic therapy other than SSA, and who are prescribed cabozantinib tablets according to the SmPC prior to entry into the study will be included in Austria and Germany.

Further details of the study population are provided in Section 5.

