Abbreviations: AE=Adverse Event; CR=Complete Response; DCR=Disease control rate; ECOG=Eastern Cooperative Oncology Group; eCRF=electronic Case Report Form; EORTC=European Organisation for Research and Treatment of Cancer; EoS=End of Study; FU=Follow-Up; HrQoL=Health-related Quality of Life; NETs=Neuroendocrine tumours; PD=Progressive Disease; PR=Partial Response; PSP=Patient Support Program; QLQ-C30=Core Quality of Life Questionnaire; QLQ-GINET21= Quality of Life Questionnaire module for GI-NET patients; SD=Stable Disease; TA=Tumour Assessment.

IPSEN GROUP CONFIDENTIAL CONFIDENTIAL

PROTOCOL FINAL V1.0: 30 JULY 2025 PAGE 22/52

All data will be recorded as applicable and available during standard of care routine: if a specific diagnostic procedure is done according to clinical routine the corresponding data should be recorded in the eCRF, otherwise the corresponding part of the eCRF will be marked as not done.

- ^a EoS visit for participants still on cabozantinib treatment after 18 months.
- ^b Combined FU/EoS visit for participants who discontinued cabozantinib early (up to 15 months after Visit 1) and subsequent therapy switch.
- ^c Enrolment in the study is possible if cabozantinib treatment started up to 4 weeks prior to enrolment. See Section 4.1.
- ^d Clinical and/or TA via imaging to determine SD, PR, CR and PD. The type of assessment must be recorded in the eCRF.
- ^e The baseline radiological tumour assessment should be the most recent TA prior to enrolment.
- ^f In case of PD and cabozantinib treatment discontinuation and subsequent therapy switch, only the FU visit must be performed 3 months after end of cabozantinib treatment. Of note, cabozantinib treatment beyond progress is possible; in this case the participant is not passed over to the FU period but remains in the 18-month observation period. In addition, also other reasons e.g. drug intolerability or adverse events might lead to cabozantinib treatment discontinuation and switch to subsequent treatment; in these cases, also only the FU visit must be performed 3 months after end of cabozantinib treatment.
- g Including recording of dose modifications, overdoses, treatment interruptions and permanent study discontinuations along with the reason for discontinuation.
- h Performed if participant was enrolled up to 4 weeks after first dose of cabozantinib and Visit 1 was captured retrospectively. HrQoL baseline will then be taken.

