- ¹ Supporting measures include the recording of participation in a PSP, use of psycho-oncological support or nutritional advice.
- ^j In particular, start of new treatment, type of treatment, treatment line and DCR within 12 weeks. For the determination of the DCR after therapy switch, the last TA prior to therapy switch serves as the baseline TA.
- ^k Only AEs related to cabozantinib as assessed by investigator.

PAGE 23/52

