4.5 Study Data Collection Timing and Methods

The expected duration of the study is maximum of 36 months. The expected duration of recruitment is 18 months. Participants will be followed-up for up to 18 months of cabozantinib treatment. If cabozantinib is discontinued during the first 15 months of observation, and a subsequent therapy is started, a follow-up visit will be performed approximately 3 months after discontinuation of cabozantinib. Enrolment in the study is possible if cabozantinib treatment started up to 4 weeks prior to enrolment. The data for Visit 1 will be captured retrospectively. Starting at Visit 2 data will be collected prospectively including hrQoL baseline assessment. Patients who have started cabozantinib treatment up to 4 weeks before giving informed consent but stopped treatment during the 4 weeks may be included.

Three visit types will be performed:

- Baseline Inclusion/ Treatment Initiation Visit (Visit 1)
- Regular visit during the observational period (Visits 2 to 9) approximately every month until Month 3 and every 3 months afterwards
- Follow-up visit for participants discontinuing cabozantinib treatment during the 15-month observational period

All data will be recorded as applicable and available during standard of care routine. If a specific diagnostic procedure or assessment is done according to clinical routine the corresponding data should be recorded in the eCRF, otherwise the corresponding part of the eCRF will be marked as not done / not available.

The timing of the visits according to routine clinical practice is assumed to be close to the proposed schedule. If the timing does not meet the schedule, entries should be made at the visit nearest in time to the proposed schedule.

For regular visits during the observation period the minimum information that must be recorded is the most recent result of the tumour assessment at/before Visit 1 to obtain a baseline value required for determination of the primary endpoint, DCR. Minimum required information for follow up visits after therapy switch, i.e. starting a new LoT includes the start date of new treatment (partial dates are allowed) and the type of treatment.

Adverse events (including treatment-emergent nonserious AEs and serious adverse events (SAEs)) and Special Situations (SS) including pregnancy will be collected during the observation period, see Section 9.

Inclusion/Treatment Initiation (Visit 1)

The following data will be collected:

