The DCR at 3 months after the switch to the next LoT will be analysed similarly to the primary endpoint, except that the population of analysis will be the FAS for participants who switched to the next LoT.

PAGE 36/52

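### The protocol gives two anchors for the single follow-up/end-of-study visit, the treatment switch and the stop of cabozantinib, and only the switch matches the clock of the next-line DCR

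*Protocol*

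**What the plan says.** **The endpoint.** Section 6.1.2 states: "DCR is defined as proportion of participants who within 3 months after switch to next LoT achieve CR, PR or SD". It takes the scans from the first dose of the new treatment onwards. Section 3 times the assessment "approximately 3 months after switch to next line of therapy after cabozantinib". Section 8.4.3.2 says: "The DCR at 3 months after the switch to the next LoT will be analysed similarly to the primary endpoint". Footnote j of Table 4-1 lists, for collection at the follow-up visit, "start of new treatment, type of treatment, treatment line and DCR within 12 weeks". All but footnote j name the switch or the first new dose as the origin, and footnote j is consistent with that.

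**The visit.** Section 4.1 says that participants who stop early and start a new line "will be followed up approximately 3 months after the treatment switch to collect effectiveness data for the new LoT". Elsewhere the origin is the stop of cabozantinib. In Section 4.5, "a follow-up visit will be performed approximately 3 months after discontinuation of cabozantinib". In footnote f of Table 4-1, "only the FU visit must be performed 3 months after end of cabozantinib treatment". The synopsis, the follow-up column header of Table 4-1, the follow-up-period paragraph of 4.5 and Section 4.7 use the same origin.

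**What follows the visit.** Footnote b of Table 4-1 makes the follow-up visit the end-of-study visit as well, and the table collects post-cabozantinib treatment at that visit only. Section 4.7 limits follow-up to 18 months after Visit 1.

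**The concern.** The endpoint and most descriptions of the visit run on different clocks. They coincide only when the next line starts as soon as cabozantinib stops. Otherwise the interval between the two treatments is taken out of the observed time on the new line. A site that follows the schedule table will close a participant's record earlier than a site that follows Section 4.1, so next-line DCR would be collected over different windows within one study.

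This cannot be left to the analysis plan, because a scan that falls after the last recorded visit is not in the database. What is at stake is how complete and how comparable the next-line DCR is, together with clarity on how long people who stop but do not switch are observed.

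**Working it through.** The plan gives no figure for this point. Its one computed precision figure, ±7.5% for the primary DCR with 135 evaluable participants, reproduces (1.96 × √(0.73 × 0.27 / 135) = 7.49%) but plays no part here. The check is date arithmetic and a comparison of passages.

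**Inputs**
- Endpoint window: 3 months from the switch (Sections 3, 6.1.2, 8.4.3.2); 12 weeks in footnote j of Table 4-1.
- Visit at stop + 3 months (synopsis, Table 4-1, 4.5, 4.7) or at switch + 3 months (4.1).
- Cap: 18 months after Visit 1 (4.7).
- Gap between the last cabozantinib dose and the first dose of the next line: not given anywhere, so assumed, from 0 to 8 weeks.
- 3 months taken as 91 days, that is 13 weeks.

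**Step 1: visit anchored to the stop.** Time on the new line at the visit = 91 days − gap.
- Gap 0: 91 − 0 = 91 days (13 weeks)
- Gap 1 week: 91 − 7 = 84 days (12 weeks)
- Gap 2 weeks: 91 − 14 = 77 days (11 weeks)
- Gap 4 weeks: 91 − 28 = 63 days (9 weeks)
- Gap 8 weeks: 91 − 56 = 35 days (5 weeks)

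A scan exactly 3 months after the switch falls after the visit by the length of the gap. A scan at 12 weeks falls after it once the gap exceeds 91 − 84 = 7 days.

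**Step 2: visit anchored to the switch.** Visit month = stop + gap + 3, all counted from Visit 1. The full window is seen, but the visit stays within the cap only if stop + gap ≤ 15 months.
- Stop 12, gap 2: 12 + 2 + 3 = month 17, within the cap.
- Stop 14, gap 2: 14 + 2 + 3 = month 19, beyond it. If the cap holds, 18 − 16 = 2 months on the new line are seen.
- Stop 15, gap 0.5: 15 + 0.5 + 3 = month 18.5, beyond it. If the cap holds, 18 − 15.5 = 2.5 months are seen.

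The 15-month limit and the 18-month cap fit each other under the stop anchor (15 + 3 = 18). Under the switch anchor they fit only without a gap.

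**Step 3: who has the visit.**
- All who discontinue in the first 15 months: synopsis, and the visit-type list and follow-up-period paragraph of 4.5.
- Only those who discontinue and start a new line: footnotes b and f of Table 4-1, the opening paragraph of 4.5, and 4.7 (4.1 likewise).

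Section 4.5 therefore contains both rules.

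**The case against.** The strongest reply is that the protocol already has the right anchor. Section 4.1 times the visit from the switch and names effectiveness on the new line as its purpose. Most other passages say only approximately 3 months, and 4.5 justifies the timing by the routine visit expected on the next line. A gap of about a week is harmless. Section 6.1.2 asks for control within 3 months, so an earlier scan on the new line counts, and the visit records the latest scan before it. This stands, and it limits the point to a contradiction between passages with a possible loss of data.

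Three stronger readings are tempting, and the documents do not support them.
- A reader might infer that every participant with a gap is lost before the response scan. That ignores 4.1, the approximate timing and the within-3-months wording. It also needs the roughly 3-monthly imaging interval, which the protocol states for visits on cabozantinib, to hold on the next line.
- A reader might infer that a line started more than 3 months after stopping is never recorded, so that switch frequency and time to next treatment are cut off there. That follows only if every discontinuer leaves the study at the follow-up visit. If the visit applies to switchers only, a participant who has not switched stays under observation, for up to 18 months after Visit 1.
- A reader might infer that those evaluable would be selected for scans prompted by symptoms. Nothing in the protocol bears on that.

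A change of denominator is not needed either. Next-line DCR follows the primary analysis (8.4.3.2), and 8.4.3.1 already adds a secondary calculation over the whole Full Analysis Set, which here means all switchers.

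**Conclusion.** The contradiction is real and should be reconciled. Under the stop anchor the observed time on the new line shrinks by exactly the gap: 11, 9 and 5 weeks at the last visit for assumed gaps of 2, 4 and 8 weeks. With gaps of several weeks, and if imaging on the next line is also roughly 3-monthly, the scan at about 3 months may fall after end of study. How many participants this would touch cannot be estimated, because the protocol gives no gap distribution.

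The disagreement on who has the visit is a second inconsistency in the same passages. Until it is settled, the length of observation for people who stop without switching is undefined.

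The impact is limited to descriptive secondary endpoints, without formal testing. The primary DCR and the sample size are unaffected.

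**What to change.** - Bring the synopsis (study timelines), Section 4.1, the follow-up column header and footnotes b and f of Table 4-1, both follow-up statements in 4.5, and 4.7 to one anchor that matches the endpoint. For switchers, the follow-up/end-of-study record should capture the routine tumour assessment about 3 months after the first dose of the next line.
- State once whether the visit applies to all discontinuers or only to switchers, and how long participants who stop without switching are observed.
- Reconcile the cap in 4.7: either let it extend for late switchers, or state that switchers whose stop plus gap lies beyond month 15 have a truncated window.

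The cost is a wording amendment, follow-up of switchers longer by their gap, and possibly one additional data-collection contact if a record 3 months after stopping is also kept. No procedures are added, since only routine assessments are recorded.
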